5.4.1.3 Dose reductions for toxicities that overlap between D+T and HCQ/placebo

Some toxicities overlap between dabrafenib, trametinib and HCQ/placebo making it difficult to accurately assign association. In these cases table 3 in conjunction with table 4 should be used to dose reduce in the appropriate fashion. In general HCQ/placebo dose should be reduced and if this does not reduce the toxicity to $<$ grade 2 or the toxicity returns after being reduced to $<$ grade 2 then dose modifications of both dabrafenib and trametinib will be made together. Non-hematological toxicities having an attribution to trametinib of possible, probable or definite will result in dose modifications as described below.

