5.4 Dose Modifications

5.4.1 General Instructions

5.4.1.1 Dabrafenib/Trametinib Dose Reduction Procedures

- If treatment related toxicities occur when dabrafenib and trametinib are used in combination, then both

agents should be simultaneously dose reduced, interrupted or discontinued with the exception of the following:

- Dose modifications are required for dabrafenib only (and not trametinib) for these events: pyrexia and, RAS mutation positive non-cutaneous malignancies
- Dose modifications are required for trametinib only (and not dabrafenib) for these events: left ventricular rejection fraction (LVEF) reduction, retinal vein occlusion (RVO) retinal pigment epithelial detachment (RPED) and interstitial lung disease (ILD)/pneumonitis (primarily related to trametinib).

NOTE: Dose modifications are not recommended for adverse reactions of cutaneous squamous cell carcinoma (cuSCC) or new primary melanoma.

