5.4.2 General Guidelines for Toxicities and Dose Modifications

Guidelines for specific toxicities are outlined below, but general guidelines for toxicities not listed are provided in Table 5.

Table 4: General Dose modification guidelines for dabrafenib and trametinib for toxicities attributable to only dabrafenib and/or trametinib. These are general guidelines but for specific toxicities dose modification instructions may be different and are provided in the subsequent sections.

CTCAE Grade	Action and Dose Modification
Grade 1	
 Continue dabrafenib, trametinib and HCQ/placebo at current dose level Monitor closely

CTCAE Grade	Action and Dose Modification
	
 Provide supportive care according to institutional standards
Grade 2	
 Interrupt dabrafenib and trametinib if clinically indicated, continue HCQ/placebo Monitor closely Provide supportive care according to institutional standards When toxicity resolves to Grade 1 or baseline, restart dabrafenib and trametinib treatment at current dose level
Grade 3	
 Interrupt dabrafenib and trametinib if clinically indicated, continue HCQ/placebo Monitor closely Provide supportive care according to institutional standards When toxicity resolves to Grade 1 or baseline, restart dabrafenib and trametinib both reduced by one dose level If the Grade 3 toxicity recurs, interrupt study treatment When toxicity resolves to Grade 1 or baseline, restart dabrafenib and trametinib both reduced by another dose level
Grade 4	
 Interrupt dabrafenib and trametinib, continue HCQ/placebo Monitor closely Provide supportive care according to institutional standards If event resolves to Grade 1 or baseline patient may continue dabrafenib and trametinib both reduced by one dose level If event does not resolve permanently discontinue study treatment

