5.4.3 Guidelines and Dose Modifications for Specific Toxicities

5.4.3.1 Management and Dose Modification Guidelines for Pyrexia

- Pyrexia is defined as a body temperature equal to or above 38.5° Celsius or 101.3° Fahrenheit
- Pyrexia is an adverse event associated with dabrafenib and is increased in frequency and severity in patients receiving dabrafenib in combination with trametinib. In a minority of cases, pyrexia was accompanied by symptoms such as severe chills/rigors, dehydration, hypotension, dizziness or weakness and required hospitalization
- Patients should be instructed on the importance of immediately reporting febrile episodes. In the event of a fever, the patient should be instructed to take anti-pyretics (e.g. ibuprofen or acetaminophen/paracetamol) as appropriate to control fever. The use of oral corticosteroids should be considered in those instances in which anti-pyretics are insufficient. Monitor serum creatinine and other evidence of renal function during and following severe events of pyrexia

Table 5: Management and Dose Modification Guidelines of Dabrafenib only for Pyrexia

Management and Dose Modification Guidelines of Dabrafenib only for Pyrexia	
Work up:	

 Clinical evaluation for infection and hypersensitivity, especially if pyrexia is complicated by rigors, severe chills, dehydration, etc. Laboratory work-up (should include full-blood-count, electrolytes, creatinine, BUN, CRP, liver-function tests, blood and urine culture). 	
Management:	

 Anti-pyretic treatment should be started immediately at the first occurrence. Anti-pyretic treatment may include acetaminophen (paracetamol), ibuprofen, or suitable anti-pyretic medication per institutional standards. Oral hydration is encouraged in patients without evidence of dehydration. Intravenous hydration is recommended if pyrexia is complicated by dehydration/hypotension. In patients experiencing pyrexia complicated by rigors, severe chills, etc., which cannot be controlled with anti-pyretic medication, oral corticosteroids should be started at the 2nd event and doses should be gradually increased for subsequent events. 
Prophylactic anti-pyretic treatment is recommended after the 2nd event, or after the 1st event if complicated by rigors or severe chills. Prophylactic anti-pyretics may be discontinued after three days in absence of pyrexia.
	
Notes	

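### Section 5.4 gives conflicting instructions for HCQ/placebo: overlapping toxicities are sent to a table whose title excludes them, and unlisted toxicities are sent to the pyrexia table

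*Combined protocol and SAP*

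**What the plan says.** All table numbers below are those of protocol section 5.4; section 1 has its own Tables 1 to 4.

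- **5.4.1.3** covers toxicities shared by all three drugs, where attribution is hard: "In these cases table 3 in conjunction with table 4 should be used to dose reduce in the appropriate fashion". The order follows: "In general HCQ/placebo dose should be reduced and if this does not reduce the toxicity to" below grade 2, or if the toxicity comes back, dabrafenib and trametinib are then modified together.
- **Table 4 (5.4.2)** is headed "Table 4: General Dose modification guidelines for dabrafenib and trametinib for toxicities attributable to only dabrafenib and/or trametinib". At grades 2 and 3 its first action is "Interrupt dabrafenib and trametinib if clinically indicated, continue HCQ/placebo". At grade 4 the two targeted drugs are interrupted without that qualifier, and HCQ/placebo again continues.
- **5.4.2**, just before Table 4, says that "general guidelines for toxicities not listed are provided in Table 5". The heading of that table in 5.4.3.1 is "Table 5: Management and Dose Modification Guidelines of Dabrafenib only for Pyrexia".
- **5.4.1.2**, in the text under Table 3, holds HCQ/placebo for any adverse event of grade 3 or higher until it falls to grade 1 or below. HCQ/placebo may then restart at a reduced dose.

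**The concern.** These are instructions that sites act on, and they do not agree. A site following 5.4.1.3 for a shared toxicity is sent to a table that by its title does not apply. If the site uses that table anyway, its rows tell it to keep giving HCQ/placebo, the drug that 5.4.1.3 has just told it to reduce. A site with a toxicity that has no section of its own is sent to fever management.

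HCQ against placebo is the randomised contrast. If the passages are read differently, HCQ/placebo exposure and the handling of dabrafenib and trametinib can differ between sites for the same event at the same grade. That variation would come from the document and not from the patient.

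**Working it through.** The point concerns scope and cross-references, so the check follows each pointer to its target and compares the instructions. The only arithmetic is the size of one HCQ/placebo step.

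**Step 1. Pointer from 5.4.1.3 to Table 4.** The source text covers toxicities shared by three drugs. The target's title covers toxicities due only to two of them. Shared toxicities fall outside the target's stated scope.

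**Step 2. Actions by grade for a shared toxicity.**

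| Grade | 5.4.1.3 | Table 4 | Text under Table 3 |
|---|---|---|---|
| 1 | No action implied (the aim is below grade 2) | All three drugs continue | Silent |
| 2 | HCQ/placebo reduced; D+T modified together only if that fails or the toxicity returns | D+T interrupted where clinically warranted, restarted at the current level; HCQ/placebo continues | Silent |
| 3 | As grade 2 | D+T interrupted where clinically warranted, restarted one level lower; HCQ/placebo continues | HCQ/placebo held, may restart reduced |
| 4 | As grade 2 | D+T interrupted, may resume one level lower; HCQ/placebo continues | HCQ/placebo held, may restart reduced |

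There is no conflict at grade 1. At grade 2 there are two different instructions for HCQ/placebo, and at grades 3 and 4 there are three: reduce, continue, hold. The conflict between hold and continue does not depend on overlap. The hold applies to any adverse event, so it also meets Table 4 inside that table's own scope.

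**Step 3. Pointer from 5.4.2 to Table 5.** The target deals with pyrexia and modifies dabrafenib only. The table headed as general guidelines is Table 4.

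**Step 4. Reach of the overlap conflict.** Rash, renal, hepatic, QTc, hypertension and ocular events have their own tables. Nausea, vomiting, diarrhea, abdominal pain and fatigue are listed for HCQ (8.3.10), for dabrafenib (5.3.1) and for trametinib (5.3.2), and have none. Section 5.1.4 refers gastrointestinal effects of HCQ/placebo to 5.4, which has no gastrointestinal table.

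**Step 5. Size of one step at grade 2.** From Table 3, the starting total is 2 × 600 = 1,200 mg a day and the first reduction gives 600 + 400 = 1,000 mg a day. The difference is 200/1,200 = 16.7% under 5.4.1.3, against no change under Table 4's grade 2 row. Re-escalation after resolution to grade 1 or below is allowed (5.4.1.4), so the difference need not be permanent.

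**The case against.** The best defence is that 5.4.1.3 asks for the two tables to be used together: Table 3 for the HCQ/placebo step, then Table 4 for the later dabrafenib and trametinib step. That reading is workable and fits the sequence in 5.4.1.3. But the text does not say it, and Table 4's title and its rows continuing HCQ/placebo work against it. Where the protocol wants such a sequence, it can spell it out: Table 6, for grade 2 rash, reduces HCQ/placebo first and keeps the other two drugs at the same dose.

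The Table 5 pointer is very probably a numbering slip, since the general table follows at once. A site is unlikely to manage nausea from a fever table. That makes it a minor error, but it remains one. Correcting it would still leave shared toxicities without their own table in conflict with 5.4.1.3.

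A reader might infer more than the text supports:

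- *That Table 4 reverses the order in 5.4.1.3.* It does not. It has no later HCQ/placebo reduction step, and its interruptions at grades 2 and 3 are conditional.
- *That 5.4.1.3 contradicts itself in its last sentence* ("Non-hematological toxicities having an attribution to trametinib of possible, probable or definite will result in dose modifications as described below"). That sentence names neither a drug to modify nor an order, and forwards the reader to later text, some of which (Table 6) reduces HCQ/placebo first.
- *That 5.4.1.1 also conflicts.* It has dabrafenib and trametinib modified simultaneously with each other, which 5.4.1.3 also says.
- *That HCQ/placebo is never touched under the Table 4 line.* At grade 3 or higher the hold under Table 3 would still apply on its own terms.

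**Conclusion.** The inconsistency is real and rests on the text alone. Three things need correcting: the mismatch between 5.4.1.3 and Table 4 in scope and action, the wrong table number in 5.4.2, and the clash between the grade 3 or higher hold and Table 4's grade 3 and 4 rows. It should be fixed, but it does not undermine the design.

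The size can be stated only per event: one HCQ/placebo step of 16.7% at grade 2 for a patient at the starting dose. A reader might want to turn the BAMM adverse event rates (section 1.1.4) into patients affected per arm, or a dose reduction into lost power. The documents support neither. The BAMM table pools grades 1 and 2 without giving the grade 2 share, and every BAMM patient received HCQ, so it says nothing about the placebo arm. No relation between HCQ dose and one-year PFS is given. Any loss from reducing HCQ/placebo first would also arise under a consistent protocol that chose that rule.

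Different handling between sites is an inference from the wording, not something the documents report. Whether HCQ/placebo should be reduced first is a clinical decision, and this point takes no view on it.

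**What to change.** In the next amendment:

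1. Reconcile 5.4.1.2 (text under Table 3), 5.4.1.3 and Table 4 so that one passage governs overlapping toxicities and states, by grade, the action for each of the three drugs.
2. Make the Table 4 title and the pointer in 5.4.1.3 agree on whether overlapping toxicities belong in that table. If it is meant for a later step only, say so.
3. Reconcile the grade 3 or higher hold on HCQ/placebo with Table 4's grade 3 and 4 rows.
4. Correct the table number in 5.4.2. Table 4 appears to be intended; the authors should confirm.

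The investigators choose the clinical rule in each case. The cost is protocol wording and a memo to sites, with no extra patients, visits or procedures.

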5.4.1.4 Dose Delays, Missed Doses, and Dose Reescalation

Major Events are grade 3 and 4 hematologic and non-hematologic toxicities that are not treatment related. Treatment should be delayed for major events if HCQ may further complicate the non-treatment related event. If a major event requires a delay of treatment, treatment must be delayed until toxicity is resolved (\leq Grade 2 or \leq Baseline). Missed doses do not need to be made up but the missed doses should be documented in the diaries. Dose reescalation following resolution to \leq Grade 1 toxicity is allowed.

5.4.2 General Guidelines for Toxicities and Dose Modifications

Guidelines for specific toxicities are outlined below, but general guidelines for toxicities not listed are provided in Table 5.

Table 4: General Dose modification guidelines for dabrafenib and trametinib for toxicities attributable to only dabrafenib and/or trametinib. These are general guidelines but for specific toxicities dose modification instructions may be different and are provided in the subsequent sections.

CTCAE Grade	Action and Dose Modification
Grade 1	
 Continue dabrafenib, trametinib and HCQ/placebo at current dose level Monitor closely

CTCAE Grade	Action and Dose Modification
	
 Provide supportive care according to institutional standards
Grade 2	
 Interrupt dabrafenib and trametinib if clinically indicated, continue HCQ/placebo Monitor closely Provide supportive care according to institutional standards When toxicity resolves to Grade 1 or baseline, restart dabrafenib and trametinib treatment at current dose level
Grade 3	
 Interrupt dabrafenib and trametinib if clinically indicated, continue HCQ/placebo Monitor closely Provide supportive care according to institutional standards When toxicity resolves to Grade 1 or baseline, restart dabrafenib and trametinib both reduced by one dose level If the Grade 3 toxicity recurs, interrupt study treatment When toxicity resolves to Grade 1 or baseline, restart dabrafenib and trametinib both reduced by another dose level
Grade 4	
 Interrupt dabrafenib and trametinib, continue HCQ/placebo Monitor closely Provide supportive care according to institutional standards If event resolves to Grade 1 or baseline patient may continue dabrafenib and trametinib both reduced by one dose level If event does not resolve permanently discontinue study treatment

5.4.3 Guidelines and Dose Modifications for Specific Toxicities

5.4.3.1 Management and Dose Modification Guidelines for Pyrexia

- Pyrexia is defined as a body temperature equal to or above 38.5° Celsius or 101.3° Fahrenheit
- Pyrexia is an adverse event associated with dabrafenib and is increased in frequency and severity in patients receiving dabrafenib in combination with trametinib. In a minority of cases, pyrexia was accompanied by symptoms such as severe chills/rigors, dehydration, hypotension, dizziness or weakness and required hospitalization
- Patients should be instructed on the importance of immediately reporting febrile episodes. In the event of a fever, the patient should be instructed to take anti-pyretics (e.g. ibuprofen or acetaminophen/paracetamol) as appropriate to control fever. The use of oral corticosteroids should be considered in those instances in which anti-pyretics are insufficient. Monitor serum creatinine and other evidence of renal function during and following severe events of pyrexia

Table 5: Management and Dose Modification Guidelines of Dabrafenib only for Pyrexia

Management and Dose Modification Guidelines of Dabrafenib only for Pyrexia	
Work up:	

 Clinical evaluation for infection and hypersensitivity, especially if pyrexia is complicated by rigors, severe chills, dehydration, etc. Laboratory work-up (should include full-blood-count, electrolytes, creatinine, BUN, CRP, liver-function tests, blood and urine culture). 	
Management:	

 Anti-pyretic treatment should be started immediately at the first occurrence. Anti-pyretic treatment may include acetaminophen (paracetamol), ibuprofen, or suitable anti-pyretic medication per institutional standards. Oral hydration is encouraged in patients without evidence of dehydration. Intravenous hydration is recommended if pyrexia is complicated by dehydration/hypotension. In patients experiencing pyrexia complicated by rigors, severe chills, etc., which cannot be controlled with anti-pyretic medication, oral corticosteroids should be started at the 2nd event and doses should be gradually increased for subsequent events. 
Prophylactic anti-pyretic treatment is recommended after the 2nd event, or after the 1st event if complicated by rigors or severe chills. Prophylactic anti-pyretics may be discontinued after three days in absence of pyrexia.
	
Notes	

 Escalation of dabrafenib is allowed if no episode of pyrexia is observed in the 4 weeks subsequent to dose reduction from the dose level you were on before. 
Pyrexia accompanied by hypotension, or dehydration requiring IV fluids, or severe rigors/chills in the absence of an obvious infectious cause should be reported as an SAE.
	
All Events	

 Clinical evaluation for infection and hypersensitivity Laboratory work-up Hydration as required 	
Event Management	Action and Dose Modification
1st Event	1st Event 
 Interrupt dabrafenib Continue trametinib and HCQ/placebo Once pyrexia resolves to baseline, restart dabrafenib at the same dose level 
 If fever was associated with rigors, renal failure, dehydration or hypotension, reduce dabrafenib to 100 mg BID
2nd Event:	2nd Event: 
 Interrupt dabrafenib Continue trametinib and HCQ/placebo Once pyrexia resolves to baseline, restart dabrafenib at 100 mg BID 
 If fever was associated with rigors, renal failure, dehydration or hypotension, reduce dabrafenib to 75 mg BID

3rd Event:
 
 • Within 3 days of onset of pyrexia 
 • Optimize anti-pyretic therapy 	
3rd Event:
 
 • Interrupt dabrafenib • Continue trametinib and HCQ/ placebo; start prednisone 20 mg PO qday for at least 5 days or as clinically indicated • Once pyrexia resolves to baseline, restart dabrafenib at 75 mg BID; continue prednisone 20 mg PO qday as clinically indicated 
 • If fever was associated with rigors, renal failure, dehydration or hypotension, reduce dabrafenib to 50 mg BID.

4th Event^f
 
 • Within 3 days of onset of pyrexia 
 • Optimize anti-pyretic therapy 	
4th Event:
 
 • Interrupt dabrafenib • Continue trametinib and HCQ/ placebo; start prednisone 20 mg PO qday for at least 5 days or as clinically indicated 
 • Once pyrexia resolves to baseline, restart dabrafenib reduced to 50 mg BID; continue with prednisone 20 mg PO qday as clinically indicated

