Grade 2	
 Initiate prophylactic and symptomatic treatment measures. Use moderate strength topical steroid.¹ Reassess after 2 weeks. 	
 Continue dabrafenib and trametinib at the same dose, but reduce HCQ/placebo by one dose level. If rash recovers to ≤ grade 1 within 2 weeks, increase HCQ/placebo dose to previous dose level. If no recovery to ≤ grade 1 within 2 weeks, interrupt HCQ/placebo until recovery to ≤ grade 1. Restart study treatment with HCQ/placebo at reduced dose level.² If no improvement in rash then reduce dabrafenib and trametinib by one dose level and restart the HCQ/placebo at reduced level.
Grade ≥ 3	
 Use moderate strength topical steroids PLUS oral methylprednisolone dose pack.¹ Consult dermatologist. 	
 Interrupt HCQ/placebo, dabrafenib and trametenib until rash recovers to ≤ grade 1. Restart with all three study agents reduced by one dose level If no recovery to ≤ grade 2 within 2 weeks, permanently discontinue study treatment.

1. Moderate-strength topical steroids: Hydrocortisone 2.5% cream or fluticasone propionate concentration 0.05% cream.
2. Study treatment may be escalated to previous dose level if no rash is evident 4 weeks after restarting study treatment.

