5.4.3.3 Management and Dose Modification Guidelines for Renal Insufficiency

Cases of renal insufficiency have occurred in patients receiving dabrafenib and the combination of dabrafenib and trametinib. Prior to start of study treatment, concomitant medications should be reviewed for the potential risk of inducing nephrotoxicity and concomitant medications should be modified if clinically possible.

Table 7: Management and Dose Modification Guidelines for Renal Insufficiency

Serum Creatinine Level	Adverse Event Management	Action and Dose Modification
Serum creatinine increase > 0.2 mg/dL (18 umol/L) but ≤ 0.5 mg/dL (44 umol/L) above baseline	
 Recheck serum creatinine within 1 week Serum creatinine increase > 1 week: contact Study chair. If elevation persists beyond 4 weeks, recommend evaluation (consider renal biopsy) for etiology; consider nephrology consultation. 	Continue HCQ/placebo, dabrafenib and trametinib at the same dose level

Serum Creatinine Level	Adverse Event Management	Action and Dose Modification
	
 If pyrexia is present, treat pyrexia as per guidelines^a 	
Serum creatinine increase > 0.5 mg/dL (44 umol/L) above baseline or serum creatinine > 2 mg/dL (> 177 umol/L)	
 Monitor serum creatinine \geq 2-times per week Hospitalization may be necessary if serum creatinine cannot be monitored frequently If pyrexia is present, treat pyrexia per guidelines^a Consult nephrologist if clinically indicated Perform renal biopsy if clinically indicated, for example: 
 Renal insufficiency persists despite volume repletion Patient has new rash or signs of hypersensitivity (such as elevated eosinophil count) 	Interrupt HCQ/placebo, dabrafenib and trametinib 
 until serum creatinine recovers to baseline Restart with HCQ, dabrafenib and trametinib^b

a. NSAIDs can induce renal insufficiency, especially in patients with dehydration; encourage oral fluids or consider intravenous fluids as clinically indicated. See guidelines for pyrexia Section [5.4.3.1](#).

b. Investigator may restart at either the same or a reduced dose level of dabrafenib. Escalation of study treatment to previous dose level is allowed if another episode of renal insufficiency does not occur after 4 weeks of dose reduction. Study treatment may not be restarted if there is evidence of thrombotic microangiopathy.

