5.4.3.8 Management and Dose Modification Guidelines for Hypertension

For patient experiencing an increase in systolic and/or diastolic blood pressure that is persistent and may be associated with the study treatment, recommendations for the clinical management of hypertension are described in Table 12.

Table 12: Management and Dose Modification Guidelines for Hypertension

Hypertension	Action and Dose Modification

(Scenario A)
 
Asymptomatic and persistent^a SBP of ≥ 140 and < 160 mmHg, or DBP ≥ 90 and < 100 mmHg, or
 
Clinically significant increase in DBP of 20 mmHg (but DBP still <100 mmHg).
	
Continue dabrafenib and trametinib and HCQ/placebo at the current dose
 
Adjust current or initiate new antihypertensive medication
 
Titrate antihypertensive medication(s) during the next 2 weeks as indicated to achieve well-controlled^b BP
 
If BP is not well controlled within 2 weeks, consider referral to a specialist and go to scenario (B).

(Scenario B)
 
Asymptomatic SBP ≥ 160 mmHg, or DBP ≥100 mmHg, or
	
Interrupt dabrafenib and trametinib if clinically indicated but continue HCQ/placebo
 
Adjust current or initiate new antihypertensive medication(s)

Hypertension	Action and Dose Modification
Failure to achieve well-controlled BP within 2 weeks in Scenario A	
Titrate antihypertensive medication(s) during the next 2 weeks to achieve well-controlled BP
 
Once BP is well controlled^b, restart dabrafenib and trametinib reduced by one dose level^c and continue HCQ/placebo

(Scenario C) Symptomatic ^d hypertension or Persistent SBP \geq 160 mmHg, or DBP \geq 100 mmHg, despite antihypertensive medication and dose reduction of study treatment	
Interrupt dabrafenib, trametinib and HCQ/placebo treatment
 
Adjust current or initiate new antihypertensive medication(s)
 
Titrate antihypertensive medication during the next 2 weeks to achieve well-controlled BP
 
Referral to a specialist for further evaluation and follow-up is recommended
 
Once BP is well controlled, restart 3 study treatments reduced by one dose level^c

(Scenario D) Refractory hypertension unresponsive to above interventions, or having hypertensive crisis.	
Permanently discontinue study treatment
 
Continue follow-up per protocol.

- a. Hypertension detected in two separate readings during up to three consecutive visits

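### Table 5 (pyrexia) fixes the dabrafenib restart dose after an uncomplicated second or third event without limiting it to the current dose, so a patient already reduced for another toxicity could be restarted higher

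*Combined protocol and SAP*

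**What the plan says.** Section 5.4.1.2 sets four dabrafenib levels: 150, 100, 75 and 50 mg BID. Table 5 in section 5.4.3.1 sets the restart dose by the number of the pyrexia event. Its first three rows add a separate instruction for fever with rigors, dehydration, hypotension or renal failure, called complicated below. For uncomplicated events:

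- First event: "Once pyrexia resolves to baseline, restart dabrafenib at the same dose level". This is relative to the current dose.
- Second event: "Once pyrexia resolves to baseline, restart dabrafenib at 100 mg BID".
- Third event: "Once pyrexia resolves to baseline, restart dabrafenib at 75 mg BID".

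The fourth-event row is worded as a reduction to 50 mg BID. The complicated instructions also name fixed doses but tell the site to reduce to them. A note in Table 5 allows dabrafenib to be escalated if the 4 weeks after a dose reduction pass without pyrexia.

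Other tables lower dabrafenib from whatever level it is at. Table 4 (section 5.4.2) takes it down one level for Grade 3 or 4 toxicity and, if a Grade 3 toxicity recurs, says "restart dabrafenib and trametinib both reduced by another dose level". For rash of Grade 3 or higher, Table 6 says "Restart with all three study agents reduced by one dose level". For hypertension, Table 12 Scenario B says "restart dabrafenib and trametinib reduced by one dose level".

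The rules for regaining a dose differ. After rash: "Study treatment may be escalated to previous dose level if no rash is evident 4 weeks after restarting study treatment". After renal insufficiency: "Escalation of study treatment to previous dose level is allowed if another episode of renal insufficiency does not occur after 4 weeks". Table 12, note c, sets a similar 4-week condition on blood pressure control. Section 5.4.1.4 permits re-escalation once toxicity has fallen to Grade 1 or lower, with no waiting period.

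**The concern.** The second- and third-event rows are entered by event count alone, yet the dose they name is absolute. A patient whose dabrafenib has already been lowered for another toxicity can be below that dose when fever recurs. A site that follows the row as written then raises dabrafenib straight after a recurrent fever, although section 5.4.3.1 describes pyrexia as associated with dabrafenib. The raise also undoes a reduction made for a different toxicity.

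The stake is dosing safety and consistency between sites. The rule is the same in both arms, and no sample size, power or error rate depends on it.

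**Working it through.** The plan gives no figure to reproduce here, so the check compares each restart dose with each possible current dose and then asks whether those states can occur.

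**1. Restart dose against current dose.** Inputs are the four levels in section 5.4.1.2 and the two fixed doses in Table 5. Change = (restart dose − current dose) / current dose.

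| Current dose (mg BID) | Uncomplicated 2nd event (100) | Uncomplicated 3rd event (75) |
|---|---|---|
| 150 | −33% | −50% |
| 100 | no change | −25% |
| 75 | (100 − 75)/75 = **+33%** | no change |
| 50 | (100 − 50)/50 = **+100%** | (75 − 50)/50 = **+50%** |

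Three of the eight cells raise the dose. In daily totals they are 150 to 200 mg, 100 to 200 mg and 100 to 150 mg. A patient at 100 mg BID is never raised.

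**2. Pyrexia alone.** Starting from 150 mg BID, the dose before the second event is 150 (uncomplicated first) or 100 (complicated first), and the row's 100 exceeds neither. Before the third event the dose is 100 (uncomplicated second) or 75 (complicated second), and the row's 75 exceeds neither. Fever by itself never produces a raise.

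**3. Pyrexia with another toxicity.** The protocol's own rules reach each raising cell:

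- 75 to 100, one other reduction: complicated first pyrexia (150 to 100), Grade 3 rash (100 to 75), uncomplicated second pyrexia (restart at 100).
- 75 to 100, no complicated fever: Grade 3 toxicity and its recurrence under Table 4 (150 to 100 to 75), uncomplicated first pyrexia (stays at 75), uncomplicated second pyrexia (restart at 100).
- 50 to 75: complicated second pyrexia (to 75), another Grade 3 toxicity (75 to 50), uncomplicated third pyrexia (restart at 75).
- 50 to 100: complicated first pyrexia (150 to 100), two reductions for other toxicities (100 to 75 to 50), uncomplicated second pyrexia (restart at 100). Without the complicated first event, three other reductions are needed.

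**4. The rows against the escalation rules.**

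- Fever within 4 weeks of the reduction: the condition in Table 5's note is not met, so the note does not allow a raise while the row states one. If the reduction was for rash or hypertension, the row can also override the 4-week condition in Table 6, note 2, or Table 12, note c.
- Fever more than 4 weeks after the reduction: the note's condition can be met, and section 5.4.1.4 also permits re-escalation after resolution. A one-level return (75 to 100, or 50 to 75) is then a permitted option, but the row states it as the restart dose.
- The 50 to 100 case moves up two levels at once.

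**5. After the fix.** With restart dose = min(current dose, row dose), current doses of 150, 100, 75 and 50 give 100, 100, 75 and 50 at the second event, and 75, 75, 75 and 50 at the third. No cell rises, and only the three raising cells change.

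**The case against.** The strongest reply is that the protocol already shows no raise is intended. Table 5's note makes escalation depend on 4 fever-free weeks and is not confined to reductions made for pyrexia. Section 5.4.1.2 labels 100, 75 and 50 mg as successive reductions. The complicated instructions and the fourth-event row speak of reducing. The text is guidance applied by a treating physician, who would be unlikely to increase the drug linked to the fever. Where the fever comes late, a one-level return is something the protocol permits anyway.

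Much of this stands. A reader might infer that nothing in section 5.4 restrains the raise. That goes too far, because the note does restrain it when fever falls within 4 weeks of a reduction. A reader might also infer that recurrent fever alone drives the dose up, and step 2 of the working shows that it does not.

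The reply does not remove the conflict. The note is a condition on escalation and not a cap on the restart dose. It gives no protection against fever that arises later, and it sits in the same table as two rows that state the higher dose without qualification. Permission to re-escalate in section 5.4.1.4 is a choice, whereas a row that names the restart dose reads as an instruction. The contrast with the first- and fourth-event rows suggests that the qualifying words were simply left out.

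**Conclusion.** The point holds as a minor gap in safety wording. For a patient already at 75 or 50 mg BID, the uncomplicated second- and third-event rows state a restart dose 33% to 100% above the current one. This contradicts Table 5's own note when the fever is within 4 weeks of the reduction. It turns an option into an instruction when the fever is later, and in one case it skips a level.

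The conclusion rests on reading the two rows as written and on applying the Table 5 note to any dabrafenib reduction, which its wording does not exclude. It also needs at least one reduction for another toxicity.

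A reader might infer that many patients are exposed or that the trial's results are at risk. The documents support neither. They give no frequency for the sequence of events required, the number of patients is probably small, and no statistical quantity is involved.

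**What to change.** In Table 5, add *or the current dose level, if lower* after the restart dose in the uncomplicated second-event and third-event rows. Leave any later increase to the existing 4-week note in the same table. The cost is one clause in two rows at the next amendment, with no added visits, procedures, patients or analyses.
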